8.3 Objectives and Endpoints

The aim of this study is to assess the effectiveness of Almega®PL on improving blood markers associated with heart health of iwi customers. Specifically, we would like to confirm the decrease in cholesterol observed in our previous trial (Rao et al., 2020) while assessing the capacity to decrease also triglycerides (primary outcome). As a secondary objective we would like to understand if EPA, precursor of signalling molecules involved in the inflammatory response, could help decrease the inflammatory marker hs-CRP.

OBJECTIVES	ENDPOINTS	JUSTIFICATION FOR
		ENDPOINTS
Primary		
,		
Can Almega®PL supplement	Triglyceride change from baseline	Triglyceride levels is
decrease triacylglycerides in a	over 6-month period.	an atherogenic lipid
generally healthy population?	-	and an important risk
9 1 9 9 1 9 1 9 1		factor in
		Cardiovascular
		Disease
Secondary		2.500.50
Secondary		
Can Almega®PL supplement	Total Cholesterol change from	Cholesterol in plasma
replicate the decrease in VLDL and	baseline over 6-month period.	levels is atherogenic
total cholesterol we observed in	VLDL-Cholesterol change from	and a risk factor in
our previous clinical trial (Rao et	baseline over 6-month period.	Cardiovascular
al., 2020)?	LDL-Cholesterol change from	Disease.
Will the results from a controlled	baseline over 6-month period.	Hs-CRP is an age
population translate to the iwi	HDL-Cholesterol change from	related inflammatory
costumers?	baseline over 6-month period.	market. Omega-3 help
Can Almega®PL supplement	hs-CRP change from baseline over	regulate the
decrease the age-related	6-month period.	inflammatory
inflammatory marker hs-CRP in a	Fasting glucose change from	response.
generally healthy population?	baseline over 6-month period.	•
	HbA1c change from baseline over	
	6-month period.	

OBJECTIVES	ENDPOINTS	JUSTIFICATION FOR ENDPOINTS

9. Study Design:

EPA is a type of omega-3 essential fatty acid known to play a beneficial role in protection against cardiovascular disease. Almega®PL is the only natural source containing EPA as sole n-3 HUFA that is available over the counter for human consumption. We **hypothesized** that AlmegaPL supplementation improves blood markers associated with heart health and inflammation. This post-market open label single armed trial involving 200-300 male and female participants, that will be monitored during the first 6 months following their subscription to Almega®PL.

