As part of the **screening procedure**, participants will complete a short questionnaire to make sure they are new iwi users. Any participant who is already using iwi will not be considered in the study. Any participant that has a serious condition (including but not limited to kidney, neurological, immunological, liver, and gastrointestinal disease, any heart condition, or diabetes) will also be disqualified for the program and directed to their doctor. Any participant attempting conception, pregnant or breastfeeding will also be disqualified. All other participants will be accepted into the limited study based on their time of application until the quota is completed. Participation in this study is purely voluntary and participants can withdraw at any point without prejudice.

Participants will be asked to take the allocated product according to the **dose** prescribed (2 capsules per day containing 1000-1100 mg Almega®PL) and adherence to the protocol will be evaluated with a follow up email. Participants will be asked to maintain their usual level of physical activity and diet for the duration of the study. The dose used in this trial is in agreement with the commercial dose communicated to the FDA and comparable to doses previously used in our clinical trials.

Along with the fist supplement order shipped to the new subscriptions, participants will receive the baseline hearth health test kit from ImawareTM. Participants will be contacted 3 and 6 months after and they will be sent subsequent kits once the confirmed adherence to the supplement. The test kits will monitor blood lipid levels across a supplementation period (baseline, month 3 and month 6) thanks to a finger prick blood drawing system. The age, height, weight, gender, fasting total cholesterol, LDL-cholesterol, HDL-cholesterol, calculated VLDL-cholesterol, triglycerides, as well as hs-CRP inflammatory marker, and glucose and HbA1c as diabetes indicator of each participant will be recorded over the study period. Qualitas Health will receive the aggregated data of the participants only for statistical analyses at their headquarter in Houston and store it in the company share drive with access restricted to those involved in the study. There will be no cost incurred for this analytical assessment to the participant.

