Results for the per protocol (PP) population will be first tested for normality before any other test will be conducted and baseline data was compared again month 3 and month 6 data. Based on the distribution of data, Welch two-sample unequal variance t-tests and Wilcoxon Ranks sum tests were used to compare two-tailed differences between groups. Differences will be considered statistically significant at a p value < 0.05. Intervention effect will also test using an analysis of covariance model (ANCOVA) adjusting for baseline parameters.

10. Study Procedures:

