### 1. Introduction

This statistical analysis plan (SAP) describes all planned analyses for the Clinical Study Report (CSR) of study **ALM-CVH-22**, a multi-center, single arm, open-label post-market evaluation of orally dosed Almega PL on cholesterol and cardiometabolic parameters.

The content of this SAP is based on protocol **ALM-CVH-22** Amendment version 2. All decisions regarding final analysis, as defined in the SAP document, have been made prior to database lock of the study data.

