Along with the fist supplement order shipped to the new subscriptions, participants will receive the baseline hearth health test kit from ImawareTM. Participants will be contacted 3 and 6 months after and they will be sent subsequent kits once the confirmed adherence to the supplement. The test kits will monitor blood lipid levels across a supplementation period (baseline, month 3 and month 6) thanks to a finger prick blood drawing system. The age, height, weight, gender, fasting total cholesterol, LDL-cholesterol, HDL-cholesterol, calculated VLDL-cholesterol, triglycerides, as well as hs-CRP inflammatory marker, and glucose and HbA1c as diabetes indicator of each participant will be recorded over the study period. **Qualitas Health** will receive the aggregated data of the participants only for statistical analyses at their headquarter in Houston and store it in the company share drive with access restricted to those involved in the study. There will be no cost incurred for this analytical assessment to the participant.

Results for the per intended-to-treat (ITT) population will be first tested for normality before any other test will be conducted and baseline data was compared against month 3 and month 6 data. Based on the distribution of data, either Welch two-sample unequal variance t-tests or Wilcoxon Ranks sum tests will be used to compare two-tailed differences between groups. Differences will be considered statistically significant at a p value < 0.05, but the thresholds for the significance of the 20 clinical outcomes were adjusted for multiple variables by the Bonferroni adjustment method which decrease the significance of p-value from <0.05, down to <0.0025. Intervention

effect will also test using an analysis of covariance model (ANCOVA) adjusting for baseline parameters.

[figure not shown]

Figure 1-1 Study design

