### 1.1. Study objectives and endpoints

4-Mar-2022

The aim of this study is to assess the effectiveness of Almega®PL on improving blood markers associated with heart health of iwi customers. Specifically, we would like to confirm the decrease in cholesterol observed in our previous trial (Rao et al., 2020) while assessing the capacity to also decrease triglycerides (primary outcome). As a secondary objective we would like to understand if EPA, precursor of signalling molecules involved in the inflammatory response, could help decrease the inflammatory marker hs-CRP.

Objectives and related endpoints are described in Table 1-1 below

Table 1.1-1. Objectives and relative endpoint

| OBJECTIVES   | ENDPOINTS   | JUSTIFICATION FOR ENDPOINTS   |
|--|---|---|
| Primary  |   |   |
| Can Almega® PL
supplement decrease
triacylglycerides in a
generally healthy
population?  | Triglyceride change from baseline over 6-month period.  | Triglyceride levels is an
atherogenic lipid and an
important risk factor in
cardiovascular disease   |
| Secondary  |   |   |
| Can Almega® PL supplement replicate the decrease in VLDL and total cholesterol we observed in our previous clinical trial (Rao et al., 2020)? Will the results from a controlled population translate to the iwi costumers? Can Almega® PL | Total Cholesterol change from baseline over 6-month period. VLDL-Cholesterol change from baseline over 6-month period. LDL-Cholesterol change from baseline over 6-month period. HDL-Cholesterol change from baseline over 6-month period. hs-CRP change from baseline over 6-month period. Fasting glucose change from baseline over 6-month period. HbA1c change from baseline over 6-month period. | Cholesterol in plasma levels is atherogenic and a risk factor in cardiovascular disease. Hs-CRP is an age-related inflammatory market. Omega-3 help regulate the inflammatory response. |

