### 2.7.2. Intention-To-Treat (ITT)

The Intention-To-Treat (ITT) will consist of a subset of participants in the database who complete at least 2 tests (baseline and month-3 test and/or month-6 test.

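### The plan tests an intervention effect by ANCOVA in a single-arm trial: there is no treatment factor to test, and the model is left open enough that several natural fits do not hold their nominal level

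*Protocol*

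**What the plan says.** The SAP introduction describes the study as "a multi-center, single arm, open-label post-market evaluation". Protocol section 9 agrees: "This post-market open label single armed trial involving 200-300 male and female participants". The primary endpoint in SAP section 1.1 (objectives table) is "Triglyceride change from baseline over 6-month period".

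The analysis paragraph in protocol section 9 ends: "Intervention effect will also test using an analysis of covariance model (ANCOVA) adjusting for baseline parameters". The corresponding paragraph in SAP section 1.1 ends the same way: "effect will also test using an analysis of covariance model (ANCOVA) adjusting for baseline parameters". Neither document says more about this model. Four things are missing:

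- the factor to be tested;
- whether the response is the visit value or the change;
- which covariates enter, and whether they are centred;
- how the three visits from one person are handled.

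The term for the covariates is not defined. Protocol section 9 lists 12 recorded variables, beginning "The age, height, weight, gender, fasting total cholesterol, LDL-cholesterol, HDL-cholesterol, calculated VLDL-cholesterol, triglycerides", and SAP sections 2.9.1 and 2.9.2 add questionnaire items such as smoking, medication use and family history.

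The analysis paragraph names the per-protocol population in the protocol and the ITT population in the SAP. The significance threshold is 0.05 in the protocol and 0.0025 in the SAP, after a Bonferroni adjustment for 20 outcomes.

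**The concern.** An ANCOVA tests a difference between groups after adjustment for covariates. Here every participant takes the product, so there is no group difference to estimate. Visit, or the intercept of a change score, has to stand in for treatment. Either one measures before-after change, which mixes any product effect with time, regression to the mean and changes in behaviour. That limit belongs to the design, and no choice of model removes it. The label *intervention effect* therefore claims more than the trial can deliver.

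The second problem is pre-specification. Because the sentence fixes neither factor, response nor covariates, the sponsor's analysts could follow it faithfully and still choose among tests with very different false-positive rates. Some are too liberal, some too strict, and one tests a quantity nobody wants.

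**Working it through.** **The plan's own figure.** SAP section 3 gives 210 for an effect size of 0.5, ratio 1 and 95% power. A two-sided two-sample t-test at 0.05 with 105 + 105 reproduces it (power 0.950). This is a calculation for two independent groups, and none is given for the ANCOVA. I use 210 below only as the number of participants.

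**Assumptions not in the documents.** Normal data, equal variances (SD = 1), no true change, the same correlation r between every pair of visits, r from 0.3 to 0.9, and ordinary least-squares standard errors. The quantity tested is month 6 minus baseline. Its true variance is 2(1 − r)/n.

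**Method.** Let k be the variance the fit reports divided by the true variance. The actual two-sided rejection rate is 2[1 − Φ(z√k)], with z = 1.960 at 5% and z = 3.023 at 0.25%.

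- *Baseline and month 6 stacked, own baseline as covariate.* The common slope is (1 + r)/2 and the mean residual variance is (1 − r)(3 + r)/4, so k = (3 + r)/4.
- *All three visits stacked, own baseline as covariate.* The slope is (1 + 2r)/3 and the mean residual variance is 4(1 − r)(2 + r)/9, so k = 4(2 + r)/9.
- *Visits stacked, covariate unrelated to the outcome.* The residual variance is 1, so k = 1/(1 − r). Rows from one person are treated as independent.
- *Intercept of change on sample-mean-centred baseline.* The residual variance is 1 − r² against a true 2(1 − r), so k = (1 + r)/2. The sampling error of the baseline mean is omitted.

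| Fit | r = 0.3 | r = 0.6 | r = 0.9 |
|---|---|---|---|
| Two visits stacked, own baseline | 7.5% | 6.3% | 5.3% |
| Three visits stacked, own baseline | 4.8% | 3.5% | 2.6% |
| Stacked, unrelated covariate | 1.9% | 0.2% | 0.0% |
| Centred intercept | 11.4% | 8.0% | 5.6% |

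Worked example, centred fit at r = 0.3: k = 0.65, z√k = 1.960 × 0.806 = 1.580, rate 11.4%.

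**Uncentred intercept.** This tests predicted change at a triglyceride value of zero, which equals (1 − r)μ even when mean change is nil. With μ = 2 SD (assumed) and r = 0.9, the standard error is √(0.19 × 5/210) = 0.0673. The expected z is 0.2/0.0673 = 2.97 and the rejection rate is 84%. At r = 0.3 and r = 0.6 it is 100%.

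**At the SAP threshold of 0.25%.** The largest rates are at r = 0.3: 0.60% for two visits stacked and 1.48% for the centred intercept. The excesses are about 0.35 and 1.2 percentage points. The uncentred intercept still rejects about 48% of the time at r = 0.9 and about 100% at r = 0.3.

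**Check by simulation.** Simulated rates agreed with these formulas within simulation error. Log-normal data gave similar results for the own-baseline stacked fits and for both intercept fits. The mixed model with unstructured covariance rejected 5.1, 4.9 and 5.1% at r = 0.3, 0.6 and 0.9 with complete data, identical to the paired t-test. It rejected 5.1 to 5.5% in the missing-visit patterns tried.

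**The case against.** The strongest reply is that the false-positive rates come from models the plan does not name. Stacking rows with a person's own baseline as both response and covariate, or testing change at a triglyceride of zero, are poor choices that a careful analyst might avoid. Regressing change on a covariate unrelated to the outcome holds about 5%. This stands: the figures show what the sentence permits, not what the sponsor will do. A reader might infer that the planned analysis has a false-positive rate of 11%, or even 100%. The documents do not support that, because they specify no fit to which such a rate could belong.

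A reader might also infer that the trial's main test fails through this sentence. The wording says the ANCOVA will be done *also*, in addition to the t-tests or rank tests, so it is supplementary. At the SAP threshold the excess in the stacked and centred fits is small in absolute terms.

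Nor do the documents hide the design. Both state one arm and open label, and protocol section 8.3.3 calls the study a cohort study rather than strictly an interventional one. It would go too far to say that readers will be misled. The narrower point survives: the label does not fit the design that the documents describe.

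Finally, dropping the ANCOVA loses the baseline-adjusted analysis. That is a real cost, though in a single arm the adjustment adds no controlled comparison.

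**Conclusion.** The point holds and should be fixed. The plan specifies a test of an effect that has no corresponding factor in a one-arm design, under a label the design cannot support, and with the model otherwise undefined. That much follows from the documents alone.

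The numbers are illustrations. They depend on the choice of fit, on r between 0.3 and 0.9, on equal correlation between visits and, for the uncentred intercept, on a mean of 2 SD. At r = 0.9 the stacked two-visit and centred fits exceed 5% by only 0.3 and 0.6 points. The larger failures are at low correlation, in fits that ignore within-person correlation, and in the uncentred intercept. Because the ANCOVA is supplementary, this does not by itself undermine the primary result.

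**What to change.** In both documents, replace the ANCOVA sentence with text along these lines: for triglycerides and each secondary endpoint, mean within-person change from baseline to month 6 (and to month 3) will be estimated from a repeated-measures mixed model with baseline, month 3 and month 6 values as responses, visit as a fixed effect and unstructured within-participant covariance, and reported with a 95% confidence interval. Name one analysis set, the same in both documents. Call the result mean within-person change.

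With complete data this equals the paired t-test. With missing visits it relies on data being missing at random, and the text should say so. The assumption matters here for two reasons. The ITT set takes participants "who complete at least 2 tests (baseline and month-3 test and/or month-6 test", and for follow-up participants are contacted and "they will be sent subsequent kits once the confirmed adherence to the supplement", so a missing result may be related to adherence.

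A model with participant and visit as two factors may look like a simpler alternative, but it should not be used for the three visits. It pools one error term and holds its level only if all visit pairs are equally correlated. If adjacent visits correlate r and baseline with month 6 r², then k = (3 + r)/(3(1 + r)). The rejection rate is then 7.1% at r = 0.3, 9.0% at r = 0.6 and 10.5% at r = 0.9.

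The cost is one sentence in each document, with no new data, visits or tests. The report gives up the intervention-effect label and the baseline-adjusted analysis.

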10.1 Treatment Schedule

Study Stage	Specific Timing	Activity
Planning	N/A	Approval of protocol
2 Months		Independent peer-review

		Logistical arrangements	
		Recruitment	
Pre-Study	Upon approval and	Preliminary screening against inclusion and exclusion criteria	
·		Pre-study interview:	
1 Month	completion	 Information email and gain informed consent from the 	
	of recruitment	participant	
		 Enrolled participants purchase the product and receive the testing kits along with instruction regarding the study requirements. 	
Study	Baseline data collection	First test kit will be shipped to imaware	
Week 0-24	Trial Period	Participant takes product as instructed	
		Participant will receive and send the test kits on month 3 and 6	
		Participant completes end-trial blood test.	
		Participants exit email or phone interview to address adherence.	
Trial			
Months 0-6			
(Period begins at	Trial end interview		
, -			
trial week 2)			
End-Study			
Month 3			
Post-Study	N/A	Data verification and statistical analysis	
		Report drafting and approval	
		Study debrief and review	
*51		receive product will only occur after all inclusion criteria have	

^{*} Please note that enrolment in the trial to receive product will only occur after all inclusion criteria have been met.

10.2 Length of Treatment Time

In total, participants will be required to send the test kits 3 times throughout the total trial time of 6 months.

At the completion of month 6, participants will repeat the baseline measures including a final blood test and a required exit interview.

Clinical interviews will be undertaken by email or phone. The trial will be completed once the last participants complete the exit interview.

10.3. Risks and Discomforts

As in the case of taking any treatment, we cannot guarantee that participants will not experience any uncomfortable effects during this study. The treatment includes the following ingredients: Almega PL.

There are 4 reported causes of adverse effects of orally dosed supplements containing EPA reported on the TGA database. Specifically, diarrhoea, dry skin, enteritis infection (inflammation of the small intestine) and nephrolithiasis (kidney stones). These events are 4 out of several thousands of participants. A 2011 study using a similar EPA based product and involving 229 participants found the product to be well tolerated.

There is also a risk of discomfort that may be experienced because of the blood draws with finger prick. Blood sampling can cause pain, bleeding, bruising, and/or swelling at the site of needle penetration (risk less than 1 in 50). Fainting may occur (risk less than 1 in 100), and infection rarely occurs (risk less than 1 in 1000).

Should participants experience any of these or other mild adverse effects or have other concerns about the treatment, blood collection, or data collection please contact the investigators (24 hours a day). Our contact details are found in the Contacts section of this document and the 24-hour contact mobile number is also on the product label.

10.4. Voluntary Participation/Right to Refuse or Withdraw

There is no obligation for participants to be involved in this study. If participants decide to participate in the study and later feel they no longer wish to be part of it, participants may withdraw from the study at any time without prejudice to any current or future involvement in clinical studies held by the study investigators or sponsor. If participants withdraw their consent, all data collected up until that time will be used in the analysis of the data.

All communications will be performed by a trained iwi Qualitas employee (Study Director) or the Principal Investigator [name]. In the event that [name] does not screen the participant, [name] will review case files before participants are enrolled. Any participant that presents a response or result (e.g. blood test) that is outside of normal range will be directed by Imaware™ to medically trained professionals with their results.

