10.6. Termination of the Study

This research project may be stopped for a variety of reasons.

During the trial, any participant that records out-of-range analytical levels will be referred to their GP for assessment of suitability/safety for continuation in the trial.

At the discretion of the GP the participant will either be placed on standard care of cholesterol-lowering medication (and removed from the trial) or continue in the trial on the supplementation.

The participant also has the option to stop supplementation at any point.

11. Investigator Benefits

The investigators are being remunerated to conduct this study. They will not allow a conflict of interest to compromise their position or this research study.

12. Consent

The Principal Investigator, [name], is required to provide participants with all information regarding the nature and purpose of the research study, risks/benefits, and the possibility of alternative treatment; participants should be given the opportunity to discuss these. It must be stated that participants are free to withdraw anytime and that if participants do not participate, they will not suffer any prejudice.

13. Advice and Information - Contact Details

If participants have any further questions regarding this study, please do not hesitate to contact:

[name] –Trial Contact Ph: [contact]

24hr [contact]

If unwarranted side effects occur, please don't hesitate to contact a doctor and the study representative. In the case of an emergency please dial 911.

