### 2.9. Patient disposition, disease history and medical history

### 2.9.1. Basic health and background data

Health and baseline disease characteristics data, as characterized by the questionnaire will be summarized and listed. Categorical data, (e.g., gender, smoking, level of physical activity, medication use, etc.) will be summarized and the percentage of participants who answer "yes" to the set questions will be calculated. Continuous data, e.g., age, weight, height, body mass index, will be summarized by descriptive statistics (N, mean, median, standard deviation, minimum and maximum). BMI (kg/m2) will be calculated as weight[kg] / (height[m]2) using weight at Baseline.

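### The handling of out-of-range results is described in two unreconciled ways, and nothing ensures that a resulting start of lipid-lowering medication becomes known to the study or is handled in the analysis

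*Protocol*

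**What the plan says.** Two places deal with abnormal results.

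- **Protocol 10.4 (repeated in SAP 2.8).** Such a participant is directed by the test company "to medically trained professionals with their results". No consequence for trial participation is given.
- **Protocol 10.6 (repeated in SAP 2.10).** During the trial, such a participant "will be referred to their GP for assessment of suitability/safety for continuation in the trial". Who makes the referral is not stated. The GP may let the participant continue on the supplement, or the participant is "placed on standard care of cholesterol-lowering medication (and removed from the trial").

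Other text bears on whether the outcome becomes known:

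- **Kits.** Protocol section 9 (Study Design) has participants contacted at months 3 and 6, and "they will be sent subsequent kits once the confirmed adherence to the supplement".
- **Exit interview.** Protocol 10.1 gives adherence as its purpose.
- **Medication.** SAP 2.9.1 lists it among questionnaire items on basic health and background: "Categorical data, (e.g., gender, smoking, level of physical activity, medication use, etc.) will be summarized". No later update is mentioned.
- **Data flow.** Protocol section 9 says the sponsor "will receive the aggregated data of the participants only for statistical analyses". SAP 2.12 has the test company supply a results sheet after laboratory analysis. Protocol 10.5 says data are identifiable by study number.
- **Analysis sets.** SAP 2.7.1 requires all three tests for the per-protocol set. SAP 2.7.2 requires baseline plus at least one later test for the ITT set.

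**The concern.** The removal rule depends on a decision made by a clinician outside the study. For the rule to work, that decision has to come back to someone who can act on it, and the analysis has to say what happens to values measured after a drug start. The documents provide neither step.

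The primary endpoint is the change in triglycerides from baseline, and total, LDL, HDL and VLDL cholesterol are secondary. A drug started because a lipid result was abnormal acts on these same measurements. With no control arm, a fall caused by the drug cannot be told apart from a fall caused by the supplement. An unrecorded start therefore pushes the result towards the hoped-for conclusion.

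**Working it through.** **Step 1: the two texts side by side.**

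- Who refers: the test company in 10.4; not stated in 10.6.
- To whom: unspecified medical professionals in 10.4; the participant's own GP in 10.6.
- Effect on participation: none stated in 10.4; continuation, or medication with removal, in 10.6.

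The texts differ on all three points, and the SAP carries both forward unchanged.

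**Step 2: follow one participant through the plan.** Suppose the month-3 lipids are abnormal, the GP starts a lipid-lowering drug, and the participant keeps taking the supplement.

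- The month-6 kit depends on adherence to the supplement, so this participant qualifies for it.
- The exit interview addresses adherence, so no stated question brings out the drug.
- The background questionnaire has already been completed, and no update is stated.
- The results sheet carries laboratory values. No abnormal-result flag, transfer timing or medication field is described.
- Three tests are complete, so the participant meets the definitions of both the ITT and the per-protocol set.

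The same holds for a drug started after an abnormal baseline result. An abnormal month-6 result cannot cause this problem, because no study measurement follows it.

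**Step 3: size of the bias.** The documents give no rate of abnormal results, referrals or drug starts, so the inputs are assumptions. Let f be the share of analysed participants who start a drug unrecorded and d the extra percentage fall in triglycerides it causes in them. The spurious mean fall is f × d.

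- Low end: 0.05 × 10% = 0.5 percentage points.
- High end: 0.20 × 30% = 6 percentage points.
- Lower uptake: 0.02 × 10% = 0.2 percentage points.

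**Step 4: effect on the false-positive rate.** The plan's own design figure is 210 participants (SAP section 3). It reproduces: a two-sided two-sample t-test with effect size 0.5, alpha 0.05 and 95% power needs 104.93, so 105 per group and 210 in total (power 0.9501). SAP section 3 states no alpha, so 0.05 is taken from the analysis text. The point does not depend on this calculation; 210 only supplies a sample size.

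Express the drug's extra effect as m standard deviations of the change, so the bias is b = f × m. For a one-sample test of change with no true supplement effect, the two-sided rejection rate at 0.05 is approximately Φ(b√210 − 1.96) + Φ(−b√210 − 1.96), with √210 = 14.49:

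- f = 2%, m = 0.25: b = 0.005, rate 0.051
- f = 5%, m = 0.5: b = 0.025, rate 0.065
- f = 10%, m = 0.5: b = 0.05, rate 0.11
- f = 20%, m = 0.5: b = 0.10, rate 0.31

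At the SAP's Bonferroni threshold of 0.0025, the last case gives about 0.06. The effect runs from negligible to serious depending on quantities the documents do not supply.

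**The case against.** The strongest reply is that the plan does deal with medicated participants, since Protocol 10.6 says they are removed. A reader might infer from the missing reporting step that removal cannot be carried out, or that everyone put on medication stays in the trial. The documents do not support that. They are silent on the mechanism, and silence does not make removal impossible. A participant may volunteer the information at the month-3, month-6 or exit contact, and Protocol 10.4 assigns communications to the study director or principal investigator.

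A reader might also infer that the study never sees abnormal results. That is not supported either. Results reach the sponsor, data are identifiable by study number, and nothing defers the transfer to the end of the study. What is missing is a stated flag and timing, and the GP's decision.

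Nor are the two referral texts strictly incompatible. A GP is a medically trained professional, Protocol 10.4 does not say the professionals belong to the test company, and 10.6 can be read as the more specific text. They are unreconciled rather than flatly contradictory.

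Finally, the uptake and drug-effect ranges have no basis in the documents, and people with diabetes or any heart condition are excluded, so uptake may be low. It is tempting to estimate how many participants would be flagged by treating the analytes and repeat tests as independent. That assumption is not credible: VLDL is calculated, the lipid fractions are related, glucose and HbA1c are related, and the tests are repeated in the same people. A flag is also not a drug start, so no such estimate is used here.

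These replies limit the claim. They do not supply the missing step: no document requires a medication question during follow-up, and no analysis rule covers values measured after a drug start.

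**Conclusion.** The point holds in limited form. The two descriptions differ in who refers, to whom and with what effect on participation, and the sponsor must reconcile them; which clinical route is right is not judged here. Removal after a drug start is stated but not assured, and medicated participants may enter either analysis set undetected.

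The spurious fall of 0.5 to 6 percentage points in mean triglycerides rests wholly on the assumed 5-20% uptake and 10-30% drug effect. It also assumes that the drug's effect adds to any supplement effect and that the starts go unrecorded. Lower uptake makes it negligible. The false-positive figures further assume a one-sample test of change in 210 people with an unchanged standard deviation. This is a cheap improvement worth making; the documents do not show that the result would be invalid without it.

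**What to change.** 1. Reconcile Protocol 10.4 and 10.6, and SAP 2.8 and 2.10 with them, into one text. It should say who makes the referral and how its outcome is reported to the principal investigator or study director.
2. At the existing month-3, month-6 and exit contacts, ask about any new lipid- or glucose-lowering medication and record it with its start date.
3. In the SAP, mark values measured after that date, and report the primary triglyceride result with and without them, together with the number of participants affected.

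The cost is a small administrative load and one extra analysis. Protocol 10.5 describes release of information in aggregated, non-identifiable form, so the sponsor may also need to check that the consent wording covers the recorded item.
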